##### **3.1.1. All Randomized/Enrolled Analysis Set**

The All Randomized/Enrolled Analysis Set includes all subjects who were randomized (Group 1 and 2) or enrolled (Group 3-5) in the study. Subjects are grouped within the All Randomized/Enrolled Analysis Set by the treatment group to which they were randomized (Group 1 and 2) or enrolled (Group 3-5).

##### **3.1.2. Full Analysis Set**

The Full Analysis Set (FAS) includes all subjects who were randomized to Groups 1 or 2, or enrolled in Group 3-5, and who took at least 1 dose of any study drug. The study drugs in this study are GS-9992 and TAF. Subjects are grouped within FAS by treatment group to which they were randomized or enrolled.

This is the primary analysis set for efficacy analyses.

##### **3.1.3. Safety Analysis Set**

The Safety Analysis Set includes all subjects who took at least 1 dose of any study drug. Subjects are grouped within the Safety Analysis Set according to the treatment they actually received.

This is the primary analysis set for safety analyses.

### **3.1.4. TFFU Analysis Set**

The TFFU Analysis Set includes all subjects who continued in the study following the discontinuation of TAF (Groups 1-3, and 5) or commercially available NUC(s) (Group 4), during the Treatment-Free Follow-Up (TFFU) Phase. Subjects are grouped within the TFFU Analysis Set by the treatment group to which they were randomized.

### **3.1.5. Biomarker Analysis Set**

The Biomarker Analysis Set includes all subjects who were randomized to Groups 1 or 2 or enrolled in Group 5, and who took at least 1 dose of any study drug and have at least 1 nonmissing biomarker value for each respective biomarker.

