#### **1.4. Rationale for This Study**

Given the low rate of HBsAg loss with currently available therapies and the treatment burden associated with life-long treatment to maintain viral suppression, there is a need to identify new therapies that may provide durable HBsAg loss with a finite treatment duration. The primary objective is to evaluate the safety, tolerability and efficacy of GS-9992 in association with an oral nucleotide (NUC) HBV polymerase inhibitor (TAF or other commercially available NUC) for the treatment of CHB subjects, while also evaluating the changes in HBV specific immune responses following treatment with GS-9992.

This Phase 2 study will be conducted in subjects with CHB, who are currently not receiving treatment for CHB (can be either treatment naïve or previously treated) or are virally-suppressed on a commercially available oral NUC. Viremic subjects with CHB generally have a rapid decline in viremia in response to beginning antiviral treatment. The decrease in viral burden may allow for an increased responsiveness to immune stimulation and forms the basis for the design of Groups 1-3 and 5 in this study. To further evaluate GS-9992 ability to improve immune response, an additional group, Group 4, will enroll virally-suppressed CHB subjects on a commercially available NUC. The immune responsiveness of CHB patients has been shown to improve in patients who are on chronic suppressive antiviral therapy with less antigen burden. Virally-suppressed patients will have lower levels of HBV virions and proteins, including HBsAg, within the serum as well as lower expression of HBV antigens within infected hepatocytes. Therefore Group 4 will evaluate the potential maximal efficacy benefits of GS-9992 in virally-suppressed CHB subjects.

Further, the safety data with GS-9992 in treatment naive subjects and in virally-suppressed subjects was evaluated in a Phase 1b study SBP-9200-101 and in the ongoing Phase 2 study SBP-9200-HBV-201. Both studies support the evaluation of GS-9992 in these populations. Subjects will be stratified by HBeAg status. HBeAg status has been shown in prior studies of TDF (GS-US-174-0102 and GS-US-174-0103) to be a predictor of eventual HBsAg loss with TDF treatment irrespective of HBV genotype.

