#### 8.2.1.4. Biomarkers

The primary analysis set for biomarker analysis is the biomarker analysis set, defined as all subjects who were randomized to Group 1 or 2 or enrolled in Group 3 or 4 or 5 and who took at least 1 dose of any study drug and have at least 1 nonmissing biomarker value for each respective biomarker.

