## 1.2. Study Design

This is a Phase 2, randomized, open-label, active-controlled study to evaluate the safety and antiviral activity of GS-9992 plus TAF or commercially available NUC in CHB subjects.

Approximately 120 chronic, immune-active, HBV-infected adults without cirrhosis will be enrolled; including 100 viremic subjects not currently on HBV NUC and 20 virally suppressed subjects on a commercially available NUC.

**Groups 1 and 2:** Approximately 40 viremic subjects will be randomized in a 3:1 ratio to the following:

- Group 1: Approximately 30 subjects will be administered GS-9992 50 mg (2 × 25 mg capsules) once daily one hour before or one hour after a meal plus TAF 25 mg once daily with food for 12 weeks then TAF 25 mg once daily with food for 36 weeks
- Group 2: Approximately 10 subjects will be administered TAF 25 mg once daily with food for 48 weeks

Randomization will be stratified by HBeAg status (positive or negative) at screening with approximately 40% of HBeAg negative subjects enrolled.

**Group 3:** Approximately 30 viremic subjects will be administered GS-9992 200 mg (2 x 100mg) once daily one hour before or one hour after a meal plus TAF 25 mg once daily with food for 12 weeks then TAF 25 mg once daily with food for 36 weeks.

Approximately 40% of subjects enrolled in Group 3 will be HBeAg negative.

[figure not shown]
**Group 4:** Approximately 20 virally suppressed subjects currently being treated with a commercially available NUC(s) for CHB will be administered GS-9992 100 mg tablet once daily one hour before or one hour after a meal for 12 weeks.

Approximately 50% of subjects enrolled in Group 4 will be HBeAg negative. Subjects will remain on their current commercially available NUC(s) therapy for the duration of the study. All subjects will be followed through Week 48.

**Group 5 (Hong Kong):** Approximately 30 viremic subjects may be enrolled and assigned:

GS-9992 400 mg (2 x 200 mg tablets) once daily one hour before or one hour after a meal plus TAF 25 mg once daily with food for 12 weeks then TAF 25 mg once daily with food for 36 weeks.

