## **3.3. Strata and Covariates**

Approximately 40 subjects will be randomly assigned to Group 1 or Group 2 via the interactive voice or web response system (IXRS) in a 3:1 ratio using a stratified randomization schedule. Approximately 30 subjects will be enrolled to Group 3, 20 subjects to Group 4 and 30 subjects to Group 5. Stratification will be based on the following variable:

- HBeAg (positive, negative)

If there are discrepancies in stratification factor values between the IXRS and the clinical database, the values recorded in the clinical database will be used for analyses.

Efficacy endpoints will be evaluated by baseline HBeAg status and overall for each treatment group.

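### SAP 3.1.5 leaves Groups 3 and 4 out of the Biomarker Analysis Set without declaring a change, while protocol 8.2.1.4 includes all five groups

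*SAP*

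**What the plan says.** SAP 3.1.5 admits to the Biomarker Analysis Set subjects "randomized to Groups 1 or 2 or enrolled in Group 5, and who took at least 1 dose of any study drug", and adds that they need at least one nonmissing value for the biomarker in question.

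Protocol 8.2.1.4 has the same dosing and nonmissing-value conditions and calls this the primary set for biomarker analysis, but it covers subjects "randomized to Group 1 or 2 or enrolled in Group 3 or 4 or 5".

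The SAP's own Full Analysis Set (3.1.2) covers subjects "randomized to Groups 1 or 2, or enrolled in Group 3-5, and who took at least 1 dose of any study drug".

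The biomarker row of the schedule (protocol Appendix 2, repeated in SAP Appendix 1) covers PBMC, whole blood, serum and plasma and has no group restriction. PBMC collection depends only on whether the site has access to a processing laboratory.

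On the purpose of Group 4, protocol 1.4 says: "To further evaluate GS-9992 ability to improve immune response, an additional group, Group 4", was to enrol virally suppressed subjects.

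**The concern.** Two governing documents define the same analysis set differently, and the later one is narrower by two whole groups. A programmer working from the SAP would flag no Group 3 or Group 4 subject as belonging to the set, even though samples were scheduled for them. One of the missing groups is the 200 mg arm. The other is the only virally suppressed group, whose rationale in protocol 1.4 refers to immune response.

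A reader of the report could not tell whether this was a decision or an accident. SAP 6.4 lists only the abandoned PK analysis as a change from the protocol, SAP 7.7 reports no changes on the safety side, and the revision table in SAP 11 is empty.

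**Working it through.** **1. Planned numbers.** SAP 3.3 gives "Approximately 40 subjects will be randomly assigned to Group 1 or Group 2", which SAP 1.2 splits into about 30 and 10. For the other groups SAP 3.3 gives: "Approximately 30 subjects will be enrolled to Group 3, 20 subjects to Group 4 and 30 subjects to Group 5". SAP 1.2 gives the total: "Approximately 120 chronic, immune-active, HBV-infected adults without cirrhosis will be enrolled".

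**2. Reproducing the plan's total.** 30 + 10 + 30 + 20 + 30 = 120, as stated. The viremic groups (1, 2, 3 and 5) give 30 + 10 + 30 + 30 = 100, also as stated.

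**3. Largest possible set under each definition.**
- Protocol 8.2.1.4 (Groups 1 to 5): 120.
- SAP 3.1.5 (Groups 1, 2 and 5): 30 + 10 + 30 = 70.
- Difference: 30 (Group 3) + 20 (Group 4) = 50, and 50/120 = 41.7%.

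**4. Among subjects planned to receive GS-9992.** Groups 1, 3, 4 and 5 give 30 + 30 + 20 + 30 = 110. The SAP set keeps 30 + 30 = 60, so 50/110 = 45.5% are left out.

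**5. Comparison with the other SAP analysis sets.**
- All Randomized/Enrolled (3.1.1): names Groups 1 and 2 and Groups 3 to 5.
- Full Analysis Set (3.1.2): names Groups 1 and 2 and Groups 3 to 5.
- Safety (3.1.3): no group limit.
- Treatment-free follow-up (3.1.4): Groups 1 to 3 and 5 by stopping TAF, Group 4 by stopping its NUC, so all five are covered.
- Biomarker (3.1.5): Groups 1, 2 and 5 only.

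The Biomarker set is the only one that loses a group. Its wording differs from that of the Full Analysis Set mainly in naming Group 5 where the other names Groups 3 to 5.

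**6. Whether sampling explains the gap.** It does not. Where the schedule limits a procedure by group, a footnote says so: genotyping is for Groups 1 to 3 and 5, and Group 4 PK sampling stops at Week 12. The biomarker row has no such note.

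**7. Where the set is visibly used.** SAP 4.1 lists it as a category in the disposition summary. SAP 3.1 requires, for every set, counts of subjects included and excluded with reasons, by treatment group. No other use can be read.

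**The case against.** The strongest reply is that the narrowing may have been deliberate and explained in text we cannot see. Material just before SAP 6.4 and after protocol 8.7 is blacked out. SAP 6.4 is headed as covering efficacy analyses, so an exploratory biomarker restriction need not appear there. The same section shows that analyses were cut after development of GS-9992 stopped. This stands as a reason not to call the slip proven. It does not remove the contradiction between the two definitions, and an intended restriction should still be declared where a reader can find it.

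Three stronger readings are tempting and should be resisted.

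- A reader might infer that the plan's biomarker comparison across 50, 200 and 400 mg loses its middle dose. No readable section plans such a comparison, and Groups 3 and 5 were assigned rather than randomized.
- A reader might infer that the purpose of Group 4 goes unanswered. Protocol 1.4 does mention immune response, but it concludes that Group 4 will assess the drug's maximal efficacy benefit. The group's primary endpoint is HBsAg decline, analysed in the Full Analysis Set, which includes it.
- A reader might infer that no biomarker table will cover the 200 mg or suppressed subjects. That follows only if those tables use this set, and the relevant text is redacted. The exclusion summary required by SAP 3.1 would also make the omission visible in the report.

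**Conclusion.** The conflict is real: protocol 8.2.1.4 includes Groups 1 to 5, SAP 3.1.5 includes only Groups 1, 2 and 5, and no readable text accounts for the difference. A drafting slip is the likeliest explanation, given the unrestricted sampling schedule and the wording of the other sets.

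The size is at most 50 of 120 planned subjects, all of Groups 3 and 4. This is a ceiling based on planned enrolment. Actual membership depends on enrolment, on dosing and on having a nonmissing value for each biomarker, and PBMC samples come only from some sites.

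The known effect is on the disposition and set-inclusion summaries; an effect on exploratory biomarker outputs is conditional on their using this set. Efficacy runs on the Full Analysis Set and safety on the Safety Analysis Set. Both include Groups 3 and 4, so the primary, secondary and safety analyses are unaffected. The point merits correction but does not threaten the trial's main results.

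**What to change.** In SAP 3.1.5, replace the reference to enrolment in Group 5 alone with enrolment in Groups 3 to 5, as the Full Analysis Set already has it. This restores agreement with protocol 8.2.1.4. Record the edit in the SAP 11 revision table or, if the SAP is already final, in the study report, as SAP 1 provides.

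If Groups 3 and 4 were left out on purpose, keep the definition but state the restriction and its reason as a change from the protocol.

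The cost is a one-phrase edit. No new data collection is needed, because sampling was scheduled in all groups. Any set flag or table already programmed on the narrow definition would have to be rerun.

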## **3.2. Subject Grouping**

For analyses based on the All Randomized/Enrolled Analysis Set or FAS, subjects will be grouped according to the treatment to which they were randomized or enrolled. For analyses based on the Safety Analysis Set, PK Analysis Set **CCI**, subjects will be grouped according to the actual treatment received. The actual treatment received will differ from the randomized or enrolled treatment only when their actual treatment differs from randomized or enrolled treatment for the entire treatment duration.

## **3.3. Strata and Covariates**

Approximately 40 subjects will be randomly assigned to Group 1 or Group 2 via the interactive voice or web response system (IXRS) in a 3:1 ratio using a stratified randomization schedule. Approximately 30 subjects will be enrolled to Group 3, 20 subjects to Group 4 and 30 subjects to Group 5. Stratification will be based on the following variable:

- HBeAg (positive, negative)

If there are discrepancies in stratification factor values between the IXRS and the clinical database, the values recorded in the clinical database will be used for analyses.

Efficacy endpoints will be evaluated by baseline HBeAg status and overall for each treatment group.

## **3.4. Examination of Subject Subsets**

Due to the exploratory nature and the small sample size of this study, subgroup analyses based on the presumed prognostic baseline characteristics will not be performed for analysis of efficacy endpoints.

## **3.5. Multiple Comparisons**

Adjustments for multiplicity will not be made, because no formal statistical hypothesis testing will be performed in this study.

### **3.6. Missing Data and Outliers**

#### **3.6.1. Missing Data**

In general, missing data will not be imputed unless methods for handling missing data are specified. Exceptions are presented in this document.

A missing baseline laboratory result will be treated as normal (ie, no toxicity grade) for the laboratory abnormality summary.

Both the baseline and post-baseline borderline results for HBeAg, hepatitis B e antibody (HBeAb), HBsAg, and hepatitis B surface antibody (HBsAb) will be imputed following the rules below:

- HBsAb/HBeAb borderline → HBsAb/HBeAb negative
- HBsAg/HBeAg borderline → HBsAg/HBeAg positive

For missing last dose date of study drug, imputation rules are described in Section 3.8.1. The handling of missing or incomplete dates for adverse event (AE) onset is described in Section 7.1.5.2, and for prior and concomitant medications in Section 7.4.

#### **3.6.2. Outliers**

Outliers will be identified during the data management and data analysis process, but no sensitivity analyses will be conducted. All data will be included in the data analysis.

### **3.7. Data Handling Conventions and Transformations**

The following conventions will be used for the imputation of date of birth when it is partially missing or not collected:

- If only month and year of birth is collected, then “15” will be imputed as the day of birth
- If only year of birth is collected, then “01 July” will be imputed as the day and month of birth
- If year of birth is missing, then date of birth will not be imputed

In general, age collected at Day 1 (in years) will be used for analyses and presented in listings. If age at Day 1 is not available for a subject, then age derived based on date of birth and the Day 1 visit date will be used instead. If an enrolled (or randomized) subject was not dosed with any study drug, the enrollment (or randomization) date will be used instead of the Day 1 visit date. For screen failures, the date the first informed consent was signed will be used for the age derivation. Age required for longitudinal and temporal calculations and analyses (eg, estimates of creatinine clearance, age at date of AE) will be based on age derived from date of birth and the date of the measurement or event, unless otherwise specified.

Non-PK data that are continuous in nature but are less than the lower limit of quantitation (LOQ) or above the upper LOQ will be imputed as follows:

- A value that is 1 unit less than the LOQ will be used to calculate descriptive statistics if the datum is reported in the form of “< x” (where x is considered the LOQ). For example, if the values are reported as < 50 and < 5.0, values of 49 and 4.9, respectively, will be used to calculate summary statistics. An exception to this rule is any value reported as < 1 or < 0.1, etc. For values reported as < 1 or < 0.1, a value of 0.9 or 0.09, respectively, will be used to calculate summary statistics.
- A value that is 1 unit above the LOQ will be used to calculate descriptive statistics if the datum is reported in the form of “> x” (where x is considered the LOQ). Values with decimal points will follow the same logic as above.
- The LOQ will be used to calculate descriptive statistics if the datum is reported in the form of “≤ x” or “≥ x” (where x is considered the LOQ).

For HBV DNA, if the value in IU/mL is above the upper LOQ, the corresponding diluted HBV DNA value, if available, will be used.

If methods based on the assumption that the data are normally distributed are not adequate, analyses may be performed on transformed data, eg, log-transformed data, or nonparametric analysis methods may be used, as appropriate.

Natural logarithm transformation will be used for plasma/blood concentrations and analysis of PK parameters. Plasma concentration values that are below the limit of quantitation (BLQ) will be presented as “BLQ” in the concentration data listing. Values that are BLQ will be treated as 0 at predose time points, and one-half the value of the LOQ at postbaseline time points.

The following conventions will be used for the presentation of summary and order statistics:

- If at least 1 subject has a concentration value of BLQ for the time point, the minimum value will be displayed as “BLQ”.
- If more than 25% of the subjects have a concentration data value of BLQ for a given time point, the minimum and Q1 values will be displayed as “BLQ”.
- If more than 50% of the subjects have a concentration data value of BLQ for a given time point, the minimum, Q1, and median values will be displayed as “BLQ”.
- If more than 75% of the subjects have a concentration data value of BLQ for a given time point, the minimum, Q1, median, and Q3 values will be displayed as “BLQ”.
- If all subjects have concentration data values of BLQ for a given time point, all order statistics (minimum, Q1, median, Q3, and maximum) will be displayed as “BLQ”.

PK parameters that are BLQ will be imputed as one-half LOQ before log transformation or statistical model fitting.

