In Cohort 1 (25mg) there were Male 12: Female 8, mean age 40.5 years with 18 Asians and 2 Caucasians. 11 were HBeAg-positive and 9 HBeAg-negative, genotype A 2, B 9, C 7 and D 2. Baseline viral burden was higher in HBeAg+ (mean HBV DNA 7.1 log10; mean quantitative HBsAg 4.38 log10) compared to the HBeAg- patients (mean HBV DNA 5.5 log10; mean quantitative HBsAg 3.18 log10). There were no clinical, hematological or biochemical SAEs and no interferon-like side effects. 11 patients had treatment-emergent AEs and there was no notable difference in the number or type of AEs between GS-9992 or placebo patients with the most common (20%) being non-specific GI complaints of constipation, abdominal pain, nausea and diarrhea. All AEs were graded mild to moderate. Three patients had ALT flares > 200 IU. Two placebo patients had viral flares including an HBeAg-neg reversion to HBeAg-pos; the other flare was immune related at week 4 in a patient on GS-9992 who had an associated 2.32 log10 reduction in HBV DNA and a 1.01 log10 reduction in HBsAg. All 3 patients were dose-reduced to every other day.

In Cohort 2 (50mg), all subjects were Asian. Subjects administered GS-9992 50mg were primarily HBeAg positive (68.8%, n=11) and male (87.5%, n=14). The average age was 39.7 years old (SD = 11.80, range 19-61), and the average BMI at baseline was 23.88 (SD = 4.440, range 17.0-31.1). The median treatment duration was 12.10 weeks with range (0.3-12.3) weeks and the average daily dose was 46.21 mg (SD: 5.117; range [35-50]). Two subjects had dose modifications due to adverse event and 1 due to the subject decision. Eleven subjects (68.8%) had at least one TEAE. The most commonly reported (>1 subjects) TEAE were headache (n=2), fatigue (n=2), ALT (n=2) and AST elevations (n=2). Four subjects (25.0%) had at least one TEAE related to study treatment. Two subjects had at least 1 TEAE leading to discontinuation of the study treatment. One subject discontinued study treatment,

GS-9992, due to a TEAE of elevated ALT > 10 ULN and switched to tenofovir with resolution. The second patient withdrew from the study and discontinued study treatment at Week 2 due to a TEAE of a mild headache.

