## 6. EFFICACY ANALYSES

### 6.1. Primary Efficacy Endpoint

#### 6.1.1. Definition of the Primary Efficacy Endpoint

The primary efficacy endpoint is the proportion of subjects with  $\geq 0.5 \log_{10}$  IU/mL decline in qHBsAg from baseline at Week 12.

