### **HBV Serology definitions:**

- **HBsAg loss:** HBsAg changing from positive at baseline to negative at any postbaseline visit.
- **Confirmed HBsAg loss:** HBsAg loss confirmed by any 2 consecutive results.
- **HBsAg loss reversion:** Any postbaseline HBsAg positive result following HBsAg loss.
- **HBsAb seroconversion:** HBsAb changing from negative or missing at baseline to positive at any postbaseline visit.
- **Confirmed HBsAb seroconversion:** HBsAb changing from negative or missing at baseline to positive at any postbaseline visit confirmed by any 2 consecutive results.
- **HBsAb seroreversion:** Any postbaseline HBsAb negative result following HBsAb seroconversion.

HBeAg-related terminology is defined similarly.

Lower LOQ (LLOQ) for HBV DNA is defined as 20 IU/mL. LLOQ for qHBsAg is defined as 0.05 IU/mL. LLOQ for qHBeAg is defined as 0.11 IU/mL.

Missing data will be treated as a non-event unless otherwise specified (eg, no HBsAg loss, no seroconversion, etc.)

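### SAP 3.7 allows a diluted value above the upper limit of quantitation for HBV DNA only, so any qHBsAg result reported as `> x` would be fixed at about the limit and could turn a true responder into a non-responder

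*SAP*

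**What the plan says.** SAP 3.7 covers non-PK data that are continuous and lie below the lower limit "or above the upper LOQ will be imputed as follows". For a result reported as `> x` the instruction is: "A value that is 1 unit above the LOQ will be used to calculate descriptive statistics". The unit follows the reported decimals. The section then adds a single exception: "For HBV DNA, if the value in IU/mL is above the upper LOQ, the corresponding diluted HBV DNA value, if available, will be used".

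The primary endpoint (SAP 6.1.1) is the proportion of subjects with at least a 0.5 log10 IU/mL "decline in qHBsAg from baseline at Week 12". SAP 6.2.1 adds a 1 log10 version and the continuous change in qHBsAg as secondary endpoints. Among the definitions in SAP 6.2.1, "LLOQ for qHBsAg is defined as 0.05 IU/mL"; no upper limit is given. Neither SAP 6.1 nor SAP 6.2 says how to score a subject whose baseline is `> x`. Protocol 8.3 treats missing data on the primary endpoint as failure.

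**The concern.** The plan foresees results above the assay range and recovers them for HBV DNA, whose change from baseline is a secondary endpoint. It does not do so for qHBsAg, which carries the primary one. The imputed value lies at the bottom of the range the true value could occupy. Applied to a baseline, it removes whatever part of a fall took place above the limit; applied to both visits, it turns any fall into zero.

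High baselines are plausible. In Cohort 1 of the earlier trial (Protocol 1.2.2), HBeAg-positive patients had "mean quantitative HBsAg 4.38" log10, about 24,000 IU/mL (10^4.38), against 3.18 log10 in HBeAg-negative patients. About 40% of viremic subjects here are to be HBeAg-negative, so about 60% should be HBeAg-positive. SAP 5.2 itself plans a baseline category above 4 log10 IU/mL. At stake are the 0.5 and 1 log10 response rates, their differences from Group 2, and the qHBsAg change over time.

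**Working it through.** The documents state no figure to reproduce. The check applies the rule directly and then sizes it under assumptions.

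**Inputs from the documents.** Threshold T = 0.5 log10 (SAP 6.1.1); HBeAg-positive and HBeAg-negative baseline means 4.38 and 3.18 log10 (Protocol 1.2.2, Cohort 1); 60/40 HBeAg mix; about 30 subjects in each viremic GS-9992 group.

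**Assumptions (not in the documents).** Upper limit U from 4.0 to 5.5 log10 IU/mL; baseline SD 0.5 or 0.8; decline distributed Normal(0.3, 0.4), independent of baseline. That gives a true response rate of 1 − Φ((0.5 − 0.3)/0.4) = 1 − Φ(0.5) = 30.9%. For orientation only, Protocol 1.2.2 reports 5 of 16 (31%) with a maximal fall above 0.5 log10 on 25 mg monotherapy.

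**Step 1: size of the added unit.** At 10,000 IU/mL, log10(10,001) − log10(10,000) = 0.00004. A censored value is in effect equal to U.

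**Step 2: who is misclassified.** Let b be the true baseline and w the true Week 12 value. The scored decline is min(b, U) − min(w, U).
- b > U and w ≤ U: scored U − w, which is less than b − w.
- b > U and w > U: scored 0.
- b ≤ U: a fall is scored correctly.

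A true responder is lost only if b > U and w > U − T. No false responder can arise while both visits are capped at the same limit. Examples with U = 4.5: a fall from 4.9 to 4.2 is truly 0.7 but scored 0.3; a fall from 5.2 to 4.6 is truly 0.6 but scored 0.0. For the 1 log10 endpoint the same condition holds with T = 1.

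**Step 3: share of true responders lost.** Simulation, 1,000,000 draws per stratum; ranges are over SD 0.5 and 0.8.

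| U (log10) | HBeAg+ baselines above U | HBeAg+ responders lost | HBeAg+ scored rate (true 30.9%) | HBeAg− responders lost |
|---|---|---|---|---|
| 4.0 | 68–78% | 56–60% | 12.5–13.6% | 2–10% |
| 4.5 | 41–44% | 24–32% | 20.8–23.4% | 0.1–3% |
| 5.0 | 11–22% | 5–14% | 26.4–29.4% | 0–0.6% |
| 5.5 | 1–8% | 0.5–5% | 29.4–30.8% | 0–0.1% |

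**Step 4: a group of 30 (18 HBeAg-positive, 12 negative).** Expected true responders: 30 × 0.309 = 9.3. Scored:
- U = 4.0: 18 × 0.125 + 12 × 0.303 = 5.9 (SD 0.5); 18 × 0.136 + 12 × 0.279 = 5.8 (SD 0.8)
- U = 4.5: 18 × 0.234 + 12 × 0.309 = 7.9; 18 × 0.208 + 12 × 0.300 = 7.3
- U = 5.0: 18 × 0.294 + 12 × 0.309 = 9.0; 18 × 0.264 + 12 × 0.307 = 8.4
- U = 5.5: 18 × 0.308 + 12 × 0.309 = 9.3; 18 × 0.294 + 12 × 0.309 = 9.0

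Each responder is 1/30 = 3.3 percentage points.

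**Step 5: effect on a difference.** Take HBeAg-positive subjects with U = 4.7, SD 0.8, and mean declines of 0.4 in one group and 0.2 in the other. The first group's 40.1% is scored as 30.8%. The second group's rate is 1 − Φ(0.75) = 22.7%; with 25.1% of its responders lost it is scored as 22.7 × (1 − 0.251) = 17.0%. The difference falls from 40.1 − 22.7 = 17.4 points to 30.8 − 17.0 = 13.8 points.

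**The case against.** **Nothing shows that a `> x` qHBsAg result will occur.** This stands. The laboratory may dilute and re-assay before reporting, in which case the rule is never triggered for qHBsAg. The HBV DNA sentence may exist only because that assay's diluted result is held as a separate record. A reader might infer from the missing provision that responders are being miscounted; the documents do not show that.

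**The rule is worded for descriptive statistics.** This also stands: using it to derive responder status is an inference. But no other rule is given. If a `> x` baseline were instead treated as missing, the missing = failure approach in Protocol 8.3 would make every such subject a non-responder, a larger loss. Either reading needs a sentence.

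**The size is assumption throughout.** Correct. A reader could settle on a limit of 4.7 to 5.1 log10 and report 3% to 25% of HBeAg-positive responders lost, but nothing in the documents selects that range. The baseline mean itself comes from 11 HBeAg-positive patients in another trial.

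**The comparison is imprecise anyway.** At an assumed 40% versus 20% with 30 and 10 subjects, the unstratified 95% half-width is 1.96 × √(0.4 × 0.6/30 + 0.2 × 0.8/10) = 1.96 × 0.155 = 30 points. No hypothesis is tested (SAP 6.1.2). This limits the consequence, but a one-directional error in the point estimate is not excused by a wide interval.

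**The rule is not aimed at the GS-9992 groups.** True. It applies to all groups alike. A group with more responders loses more of them in number, not in proportion: in Step 5 the proportional loss is 23% in the better-responding group (9.3/40.1) and 25.1% in the other.

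**Conclusion.** The gap is real and conditional. SAP 3.7 protects HBV DNA from upper censoring and leaves qHBsAg under a rule that, once triggered, gives a value known to be too low. For the 0.5 and 1 log10 endpoints the error runs one way: true responders can be lost and none gained. It falls mainly on HBeAg-positive subjects and tends to shrink differences from Group 2.

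Under the stated assumptions, 0.5% to 60% of HBeAg-positive true responders would be lost over limits of 5.5 down to 4.0 log10. In a group of 30 that runs from almost none to about 3.5 responders. The loss is zero if the laboratory always returns a dilution-corrected number. The documents support the statement that the plan can miscount responders. They do not support a statement that it does, nor any single figure for how many. The correction is cheap enough to be worth making without knowing the size.

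**What to change.** 1. Extend the exception in SAP 3.7, keeping its availability condition. For example: *Where an HBV DNA or qHBsAg result exceeds the upper LOQ, its dilution-corrected result is used when one exists, at baseline and at later visits.*
2. State the qHBsAg upper limit beside the lower limit in SAP 6.2.1, and say whether the laboratory dilutes high samples before reporting.
3. Define responder status for a baseline that remains `> x`. Count the subject as a responder if the limit minus Week 12 is at least the threshold. Otherwise flag the status as undetermined and keep the subject as a non-responder in the main analysis.
4. Cover the reverse case that item 1 opens: a diluted baseline with a Week 12 result still reported as `> x`. Setting Week 12 at the limit would then overstate the fall, so that subject should not be counted as a responder on the imputed value.
5. Report the number of censored baselines and of undetermined subjects by group and HBeAg status.

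The cost is a few SAP sentences and one small table, best in place before the interim analysis in SAP 2.1, which includes the Week 12 regimen. Repeat dilution of stored serum is optional and depends on usable samples, which cannot be confirmed from the documents.
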